1.0 Project Summary/Abstract

Acute and chronic inflammation both increase cardiovascular disease risk, especially with aging, which may be due to vascular dysfunction. Aging and inflammation also lead to increased oxidative stress, which impairs vascular function. During acute inflammation, endothelial function is altered differently in younger and older adults with decreases in endothelial function in younger, but not older adults. However, cardiorespiratory fitness is cardio-protective, impacting inflammation, vascular function, and oxidative stress. During acute inflammation, moderately fit older adults exhibit similar responses to younger adults, suggesting preserved endothelial reactivity. However, whether the protective mechanism is oxidative stress has not been confirmed. Furthermore, it is undetermined whether the vascular dysfunction is further propagated down the arterial tree during acute inflammation to the microvasculature. We will investigate these questions through 2 specific aims: 1) To determine if age and fitness moderate the vascular response to acute inflammation; 2) To determine if antioxidant administration eliminates vascular dysfunction during acute inflammation.

We will recruit 15 young low fit (18-35 years) and 30 older low or high fit (55-75 years) adults. An acute inflammatory bout will be induced by typhoid vaccination. The influence of oxidative stress will be assessed using an oral antioxidant. Baseline influences of the antioxidant on endothelial function will be assessed on Visit 1. Acute inflammation measures will be taken at baseline (Visit 2, prior to) and 24-hours after the vaccine (Visit 3). The antioxidant will be administered again on Visit 3.

We anticipate low fit older adults will have reduced endothelial responsiveness and microvascular reactivity compared to young and high fit older adults. Second, we anticipate the antioxidant will improve vascular function at baseline in low fit older adults. During acute inflammation, we anticipate improvement in vascular function to baseline levels in young and older high fit adults.

The results from this study will help to elucidate if fitness is a protective and preventive measure to ameliorate the detrimental cardiovascular response to acute inflammation. Thus, this study may provide health professionals with a behavioral intervention to reduce cardiovascular disease burden in the rapidly growing aging population.

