6.0 Study Design and Procedures

Study site

All study procedures except the vaccination will be conducted in the Integrative Physiology Laboratory at the University of Illinois at Chicago located at [name] in the Disability, Health and Social Policy building (DHSP). The typhoid vaccination will be administered by a registered nurse at the Clinical Research Center at UIC.

Design

A comparative, observational study design will be conducted with a group of 15 low fit young adults, 15 low fit older adults, and 15 high fit older adults, for a total of 45 research participants.

Subjects will participate in three study visits, with at least 72 hours between the first two visits, and exactly 24 hours between the last two visits. Menstruating females will be studied during the first 7 days of menses, or during the placebo phase if taking oral contraceptives. Participants will arrive to each visit having refrained from exercise, alcohol, and caffeine for 24h prior to each test day. Participants will be tested in the post-prandial (no food, only water) state (>10 hours) for all visits. (Figure 1)

[figure not shown]

Figure 1. Study protocol schematic

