12.0 Statistical Considerations

The data will initially be examined for normality violations, entry errors, and missing values. Entry errors will be corrected by double-checking with original data files. Non-normally distributed data will have an appropriate transformation applied to achieve normality (i.e. log transformation, square root, etc.).

All analyses will be adjusted for age, sex, and body mass index, which are all factors known to influence hemodynamic parameters. Additionally, due to multiple tests, a correction will be applied for multiple comparisons (α divided by the number of tests). Significance level will be set at $\alpha=0.05$, with a Bonferroni correction used to correct for multiple comparisons.

Aim 1: The effects of acute inflammation on endothelial and microvascular function will be tested with a two-way group (3) by time (2) repeated measures ANOVA (V2 and V3 baseline). We expect older high fit adults to have similar vascular reactivity as young adults, i.e. decreased FMD and NIRS reperfusion, suggesting that fitness maintains vascular reactivity during an inflammatory insult with age. If no difference in the response to acute inflammation is seen between low and high fit older adults (not expected), this would indicate fitness is not protective with age during acute inflammation.

Aim 2: The effects of ascorbic acid ingestion will be tested with a two-way group (3) by time (2) repeated measures ANOVA to determine if the antioxidant caused changes at Visit 1 (baseline) or Visit 3 (acute inflammation). A two-way group (3) and time (3) repeated measures (V2 baseline, V3 before and after Vit C) ANOVA will determine if the antioxidant attenuated endothelial function during acute inflammation. At baseline, we expect ascorbic acid to improve vascular function, i.e. increase FMD and NIRS reperfusion, in older low fit adults, with no changes seen in young or high fit older adults. During acute inflammation, we expect ascorbic acid to restore vascular function to baseline in young and older high fit adults. If ascorbic acid does not alter vascular function during acute inflammation, this would indicate another mechanism other than oxidative stress is contributing to vascular dysfunction.

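### With 15 per group and no confidence interval, a null test cannot show that fitness is not protective or that another mechanism is at work

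*Combined protocol and SAP*

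**What the plan says.** The design in Section 6.0 has three groups: "15 low fit young adults, 15 low fit older adults, and 15 high fit older adults".

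Section 12.0 tests Aim 1 with a group (3) by time (2) repeated-measures ANOVA on the pre-dose measurements at Visits 2 and 3. Aim 2 uses group (3) by time (2) models for the ascorbic-acid effect, and a group (3) by time (3) model whose time points are "V2 baseline, V3 before and after Vit C". Alpha is 0.05 with a Bonferroni correction; the number of tests is not given. All analyses are adjusted for age, sex and body mass index (BMI).

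The same section fixes two negative conclusions:

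- Aim 1, if the low- and high-fit older groups do not differ in response (an outcome marked as not expected): "this would indicate fitness is not protective with age during acute inflammation".
- Aim 2: "If ascorbic acid does not alter vascular function during acute inflammation, this would indicate another mechanism other than oxidative stress" contributes to the dysfunction.

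The protocol and SAP state no confidence interval, smallest effect of interest, equivalence margin or power for this study. Section 9.0 calls the study hypothesis generating and a source of data for later power analyses.

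**The concern.** Failing to find a difference is not evidence that there is none, unless the estimate is precise enough to exclude effects that matter. The only criterion Section 12.0 offers for deciding that groups do not differ, or that ascorbic acid does nothing, is the ANOVA at the stated alpha. With 15 per group such tests often miss moderate effects, yet the plan attaches a substantive conclusion to that outcome.

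The Aim 2 statement has a second gap. A null ascorbic-acid result can point away from oxidative stress only if there was a fall in function to reverse and the dose raised plasma ascorbate. Both are measured: the three-time-point model contains the Visit 2 to Visit 3 change, and Section 6.0 lists ascorbate at every blood draw. The inference is not tied to either. This matters because Section 2.0 reports that endothelial function fell during acute inflammation in younger but not in older adults, so some groups may have no fall to reverse.

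At stake is a report that fitness does not protect, or that oxidative stress is not the explanation, while a moderate effect remains compatible with the data. Later studies would be planned on that basis.

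**Working it through.** The plan gives no power or precision figure to reproduce, so the check computes what 15 per group can deliver.

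**Inputs.** From the documents: n = 15 per group (Section 6.0); alpha 0.05 before correction (Section 12.0). Assumed: two-sided tests; true effects of 0.5 and 0.8 SD of the change score, because the text gives no SD for FMD; no covariate adjustment; no dropout; a Bonferroni divisor of 3 as an illustration.

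**Aim 1, high-fit versus low-fit older adults.** For two groups and two times, the group-by-time contrast is a two-sample comparison of changes.

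- Standard error in SD units: √(2/15) = 0.365.
- 95% half-width: t(0.975, 28 df) × 0.365 = 2.048 × 0.365 = 0.75 SD.
- Noncentrality: 0.5/0.365 = 1.37 and 0.8/0.365 = 2.19.

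**Aim 2, ascorbic-acid effect within one group of 15.**

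- Standard error: 1/√15 = 0.258.
- 95% half-width: t(0.975, 14 df) × 0.258 = 2.145 × 0.258 = 0.55 SD.
- Noncentrality: 0.5 × √15 = 1.94 and 0.8 × √15 = 3.10.

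Probability of missing a true effect, from the noncentral t distribution:

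| Comparison | True effect | Alpha 0.05 | Alpha 0.05/3 |
|---|---|---|---|
| 15 vs 15 | 0.5 SD | 74% | 86% |
| 15 vs 15 | 0.8 SD | 44% | 62% |
| One group of 15 | 0.5 SD | 56% | 74% |
| One group of 15 | 0.8 SD | 18% | 35% |

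**Sensitivity to the error term.** Pooling the error over all three groups (42 df) changes little: at alpha 0.05 the misses become 73% and 43% between groups, and 53% and 14% within a group.

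**What a null leaves open.** An observed between-group difference of exactly zero has a 95% interval of −0.75 to +0.75 SD. Non-significance also covers estimates well away from zero: an observed 0.74 SD is not significant, and its interval runs from 0.74 − 0.75 = −0.01 to 0.74 + 0.75 = 1.49 SD. The verdict of no difference alone does not tell these two cases apart; the interval does.

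**The case against.** **These are discussion sentences, not decision rules.** Section 12.0 never says non-significant; it speaks of no difference being seen and of ascorbic acid not altering function. Treating that as a failed test is therefore an inference. It is a fair one, since no other criterion is given, but a reader should not report that the plan explicitly equates a p-value above 0.05 with no effect.

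**The study is hypothesis generating.** This explains the absence of a power calculation and limits the harm. A reader might infer that the trial makes an invalid confirmatory claim or is too small for its purpose; Section 9.0 does not support that. It still does not license a negative conclusion from an imprecise null.

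**A null is not uninformative.** This stands. At alpha 0.05 a 0.8 SD ascorbic-acid effect within a group is missed only 18% of the time, and an observed between-group zero excludes 0.8 SD at the 95% level. Pooling all 45 participants would narrow the ascorbic-acid half-width to t(0.975, 44 df)/√45 = 0.30 SD, but the Aim 2 hypotheses are group-specific.

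**The reactivity wording.** A reader might see a contradiction in high-fit older adults having "similar vascular reactivity as young adults, i.e. decreased FMD and NIRS reperfusion, suggesting that fitness maintains vascular reactivity", since a fall is there read as preserved function. The Project Summary uses the same sense: "moderately fit older adults exhibit similar responses to younger adults, suggesting preserved endothelial reactivity", with low-fit older adults expected to respond less. A fall in FMD can be both a preserved response and a loss from baseline, so this is not a contradiction and forms no part of the point.

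**Why not require equivalence?** With 15 per group and a true difference of zero, a 90% interval falls inside ±0.8 SD only 38% of the time, and 8% if the 5% one-sided level is divided by 3. The documents give no margin, so making no similarity claim is the sounder course.

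**Conclusion.** The point holds. If Section 12.0 is followed as written, a null result would lead to conclusions that 15 per group cannot support. Such a result argues against large effects but not against moderate ones.

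The sizes depend on effects assumed in SD units and on unadjusted two-sided tests. The planned covariate adjustment could move them either way, depending on how much variance the covariates explain and how far BMI differs between the older groups, neither of which the documents state. Any Bonferroni divisor above 1 makes misses more frequent. The logical gap depends on none of these assumptions.

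A reader might also infer that the plan overlooks the fall after vaccination or the uptake of ascorbate. It does not: both are measured. What is missing is that the mechanism inference be made to depend on them. Severity is low, because the harm is to interpretation and to the planning of later studies.

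**What to change.** Replace the two conditional conclusions in Section 12.0 with:

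> We will report the high-fit minus low-fit difference in Visit 3 minus Visit 2 change, and the ascorbic-acid effect at Visit 3 by group, with 95% confidence intervals, for FMD and NIRS. A non-significant result will be described as inconclusive, together with the range of effects the interval leaves open. It will not be taken to show that fitness is not protective, that groups are similar, or that function was restored to baseline. A null ascorbic-acid result will be discussed as pointing to another mechanism only in a group that shows a Visit 2 to Visit 3 fall (95% confidence interval below zero) and a rise in plasma ascorbate after dosing, and only as a hypothesis for later study.

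This text also covers the similarity and return-to-baseline hypotheses in Section 3.0 (1A and 2B), which a non-significant difference cannot establish either.

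The cost is rewording and the reporting of intervals; no participants, visits or assays are added. The downside is that several null results will be labelled inconclusive, and the study will make no claim of similarity or absence of effect.

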To understand the vascular response to acute inflammation, an integrative approach must be applied to identify both the mechanism of vascular dysfunction and a potential therapeutic target to abrogate acute inflammation-induced vascular dysfunction. This study addresses both gaps of knowledge by investigating the role of oxidative stress and by recruiting participants based on training levels to effectively examine the effect of high fitness.

Relevance

[figure not shown]
CV disease is the leading cause of death in the United States and particularly burdens older individuals[31]. Aerobic exercise is recommended by the United States Physical Activity Guidelines, American Heart Association, and American College of Sports Medicine (ACSM) to improve quality of life, reduce risk of heart disease, diabetes, stroke, and osteoporosis, and improve immune function. If fitness moderates the effects of acute inflammation on vascular function, our study will provide insight into how physical activity and exercise interventions could reduce the risk of CV events during acute inflammation.

Preliminary Studies

Our laboratory has conducted a series of studies evaluating the effect of acute inflammation on cardiovascular function[15–17,32–34]. evaluated both cardiac and endothelial function during acute inflammation in younger and older adults[16,17,34]. These studies suggest age-associated differences in endothelial function, cardiac function, and blood pressure that may be detrimental to older adults[16,33,34]. We have shown that fitness, an indicator of chronic exercise, may exert protective effects. In older adults, high fitness protected from acute inflammation-induced arterial stiffening[15].

Recently our lab has shown that high fit older adults also have a similar endothelial response to acute inflammation as younger adults. The high fit older adults exhibit a greater reduction in flow-mediated dilation than older low fit adults. Fitness level did not influence the response in young adults (Figure 2)[23]. Additionally, we have collected pilot data on microvascular reactivity in young adults ($n=16$), showing no changes in tissue saturation index from baseline to 24h during acute inflammation in peak hyperemic response ($13.7\pm3.9\%$ to $13.8\pm2.9\%$) or reperfusion slope ($1.84\pm0.52\%/\text{s}$ to $1.83\pm0.49\%/\text{s}$).

Figure 2

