3.0 Objectives/Aims

Aim 1: To determine if fitness moderates the vascular response to acute inflammation with aging. We hypothesize that during acute inflammation A) high fit older adults will have similar endothelial and microvascular reactivity as young adults; B) high fit older adults will have greater endothelial and microvascular reactivity than low fit older adults.

Aim 2: To determine if antioxidant administration eliminates vascular dysfunction during acute inflammation. We hypothesize A) at baseline, ascorbic acid will improve endothelial function only in low fit older adults; B) during acute inflammation, ascorbic acid will improve vascular function to baseline values in young and older high fit adults.

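### Aim 2 never tests the vitamin C change at Visit 3 against that at Visit 1, so its planned analyses cannot show that a Visit 3 effect is specific to inflammation

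*Combined protocol and SAP*

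**What the plan says.** Section 12.0 gives Aim 2 two analyses.

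- A two-way ANOVA, three groups by two times, is used "to determine if the antioxidant caused changes at Visit 1 (baseline) or Visit 3 (acute inflammation"). Its only factors are group and time.
- A second two-way model has three groups and three times: "repeated measures (V2 baseline, V3 before and after Vit C) ANOVA will determine if the antioxidant attenuated endothelial function during acute inflammation". It contains no Visit 1 data.

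Hypothesis 2A in section 3.0 is that "at baseline, ascorbic acid will improve endothelial function only in low fit older adults". Section 12.0 repeats this expectation for Visit 1, "with no changes seen in young or high fit older adults", and then expects vitamin C to bring those same two groups back to baseline at Visit 3. One rule of interpretation is written down: "If ascorbic acid does not alter vascular function during acute inflammation, this would indicate another mechanism other than oxidative stress" is at work. Section 2.0 states the wider purpose: "This study addresses both gaps of knowledge by investigating the role of oxidative stress".

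Alpha is 0.05, "with a Bonferroni correction used to correct for multiple comparisons"; the number of tests is not given. Section 9.0 calls the study hypothesis generating and adds no further test. Section 6.0 schedules endothelial and microvascular measures before and after the dose at both Visit 1 and Visit 3, and describes no placebo or time-control arm.

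**The concern.** For young and high fit older adults the predicted result is a difference between visits: nothing at Visit 1, recovery at Visit 3. The plan would see this only as two separate verdicts, and one significant and one non-significant result are not a test of the difference.

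Without a placebo or time control, Visit 1 is the only within-person reference for repeat testing, elapsed time, or a general vitamin C effect unrelated to inflammation. An effect of this kind that is equal at both visits would also lift the post-dose Visit 3 value towards the Visit 2 value. The three-time model therefore cannot separate it from reversal of inflammatory dysfunction.

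At stake is whether a Visit 3 rise is credited to oxidative stress during inflammation, and what effect size is carried into the power analyses for later studies that section 9.0 foresees.

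**Working it through.** **Is the test anywhere in the plan?** No. The first model is two-way, with group and time as its named factors, and so has no visit term. The second omits Visit 1. Section 9.0 gives only software and purpose. There is no stated power, effect size or FMD SD to reproduce.

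**Set-up (assumed values).** There are 15 per group (section 6.0), residual SD 1 per measurement, independent errors, two-sided alpha 0.05, and no covariate adjustment. Let D1 and D3 be post-dose minus pre-dose at Visits 1 and 3, and C = D3 − D1.

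- Single-visit change: SD √2, 95% half-width 2.145 × √(2/15) = 0.78.
- Contrast C: SD 2, half-width 2.145 × 2/√15 = 1.11, a ratio of about 1.4.

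**Why separate tests mislead.** If each visit has power p and the true shift is identical, the chance of significance at Visit 3 only is about p(1 − p). At a shift of 0.5 SD of a change (about 0.7 residual SD), p = 0.438, and 0.438 × 0.562 = 0.246.

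**Simulated rates (%), identical true shift at both visits:**

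| Shift (residual SD) | 0.3 | 0.5 | 0.7 | 1.0 | 1.4 |
|---|---|---|---|---|---|
| A. Visit 3 significant, Visit 1 not, in one group | 10 | 19 | 24 | 20 | 5 |
| B. A, and Visit 1 time main effect (all 45) not significant; three groups share the shift | 8 | 8 | 4 | 0.2 | 0 |
| B, two groups share it | 9 | 14 | 14 | 6 | 0.4 |
| B, one group has it | 10 | 17 | 23 | 18 | 5 |
| C. B, plus a significant Visit 2 to Visit 3 fall (set equal to the shift) and post-dose Visit 3 not different from Visit 2; three groups | 2.5 | 3.7 | 2.4 | 0.2 | 0 |
| C, two groups | 3 | 6 | 9 | 5 | 0.5 |
| C, one group | 3 | 8 | 13 | 15 | 4 |

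Rows A and B use 60,000 runs. The C rows use 20,000 and are good to about one percentage point. The direct contrast rejects in about 5% of runs in every column.

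**Sensitivity of B.**

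- At 0.05/3 (number of tests assumed): 4/6/5/0.7/0% with three groups and 4/9/13/10/2% with two.
- With the two changes correlated 0.5: 5/5/2/0.1/0% and 7/9/9/4/0.3%.

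**If low fit older adults do respond at Visit 1.** The plan expects this; a rise of 1.4 SD is assumed. The Visit 1 main effect is then significant in 87% to 100% of runs, so it no longer flags an artefact. The misleading pattern in a given other group, alongside a significant low fit rise and a significant Visit 1 interaction, occurs in 6/8/7/4% of runs at shifts of 0.3/0.5/0.7/1.0.

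**How good a control is Visit 1?** In the section 6.0 time table, taken in row order, the interval from first to second FMD start is:

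- Visit 1: 13 + 10 + 120 + 10 + 7 = 160 minutes.
- Visit 3: 13 + 10 + 15 + 5 + 15 + 120 + 10 + 7 = 195 minutes.

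The column sums match the stated totals of 285 and 245. If row order is procedure order, Visit 1 is only a partial control.

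**What the contrast costs.** For a Visit 3-only effect of 1.4 SD, power is 0.945 for the single-visit test and 0.713 for the contrast. At 0.05/6 it is 0.762 and 0.398.

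For scale, the section 2.0 pilot in 16 young adults, "showing no changes in tissue saturation index from baseline to 24h during acute inflammation", gives reperfusion slope SDs of 0.52 and 0.49 %/s on a mean of 1.84. With mean SD 0.505 and an assumed within-person correlation r of 0.5 to 0.8, the residual SD is 0.505 × √(1 − r) = 0.357 to 0.226. Multiplying by 1.108 gives a contrast half-width of 0.40 to 0.25 %/s.

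**The case against.** The strongest reply is that Aim 2 makes no claim about a difference between visits. 2A concerns baseline, 2B concerns return to baseline under inflammation, and each has its model. The only written inference rule covers a null Visit 3 result. That is right as far as the hypotheses go. But the predictions for young and high fit older adults, read with the stated purpose of investigating oxidative stress, invite the inference that a Visit 3 rise reflects inflammation.

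Second, the row A rates overstate the risk, because the whole predicted pattern must appear. This also stands. With the fall and return conditions added, the rate is below 4% when all groups share the shift, which is the natural form for a repeat-test or elapsed-time effect. It remains material for moderate shifts limited to one or two groups.

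Third, the contrast does not establish mechanism. This is true: with no vitamin C effect at all, a recovery confined to Visit 3 of 0.5 to 1.0 SD gives a positive contrast in about 14% to 44% of groups. The root limit is the lack of a placebo or time control, and the contrast removes only what is equal at both visits.

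Fourth, every magnitude is assumed, and the 160 and 195 minutes depend on a table whose layout is imperfect in the available text, while the narrative says only 2 hours at both visits. Both points are fair. The absence of the test depends on neither.

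**Conclusion.** The concern holds. No planned analysis compares the vitamin C change at Visit 3 with that at Visit 1, so the planned tests cannot support a statement that a Visit 3 effect is specific to inflammation. Certainty is high for the omission and moderate for its consequence, because the rates rest on an assumed residual SD, independent errors and equal true shifts.

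The practical risk is small for large effects shared by all groups, which the Visit 1 main effect would usually expose. It lies mainly with small-to-moderate or group-limited effects, where the complete misleading pattern can reach roughly 8% to 15%. In a hypothesis-generating study this affects interpretation and what is carried forward. It does not invalidate 2A or 2B. It should be fixed because the remedy needs no new data.

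**What to change.** Add to section 12.0 one mixed model with group × visit (1, 3) × dose status (before, after), the planned covariates (age, sex, BMI), and an unstructured covariance over the four measurements.

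- Report C = (Visit 3 post − Visit 3 pre) − (Visit 1 post − Visit 1 pre) for each group with a 95% CI, for FMD and NIRS reperfusion: 3 × 2 = 6 contrasts.
- Either count these six in the Bonferroni family or label them as estimates outside it. The second suits a hypothesis-generating study.
- Keep the three-time model for return to baseline, and read the Visit 1 main effect and interaction beside the contrast.
- Base any statement that the effect is specific to inflammation on the contrast and its CI, and do not read a null contrast as no effect.
- State what the contrast leaves unresolved: recovery after vaccination during Visit 3, regression to the mean from a low pre-dose Visit 3 value, and the longer test battery before the Visit 3 dose.

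The cost is analysis-plan wording only, since all four measurements are already scheduled. The price is precision: a standard error about 1.4 times that of a single-visit change, with the loss of power shown above.
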